8.2 SAFETY AND OTHER ASSESSMENTS

Subject Screening: The lead study coordinator, graduate student, or post-doctoral fellow will examine medical records prior to approaching patients in clinic regarding enrollment. If the study staff finds that a patient meets any of the study exclusion criteria, that patient will not be approached for enrollment into the study. If after examining medical records the patient appears to be eligible for study enrollment, study staff will approach in clinic, describe the study, and determine interest for potential enrollment. If a patient expresses interest in enrollment, they will be sent home with the study consent form and study staff will make follow-up contact within 3 days. During this contact, the staff member will screen subjects using the subject inclusion/exclusion criteria case report form to confirm eligibility. If eligibility is confirmed, study staff will schedule the first testing visit. The following information will be collected during screening:

- Date of birth
- Injury history
- Type of ACL reconstruction patient will undergo
- Date of scheduled reconstruction surgery.

8.3 ADVERSE EVENTS AND SERIOUS ADVERSE EVENTS

8.3.1 DEFINITION OF ADVERSE EVENTS (AE)

Adverse event means any untoward medical occurrence associated with the use of an intervention in humans, whether or not considered intervention-related (21 CFR 312.32 (a)).

8.3.2 DEFINITION OF SERIOUS ADVERSE EVENTS (SAE)

Serious adverse events (SAE) are defined as any event temporally associated with the subject's participation in research that meets any of the following criteria:

- Results in death;
- Is life-threatening (places the subject at immediate risk of death from the event as it occurred);
- Results in inpatient hospitalization or prolongation of existing hospitalization;
- Results in a persistent or significant disability/incapacity or substantial disruption of the ability to conduct normal life functions;
- Results in a congenital anomaly/birth defect;
- Any other adverse event deemed to jeopardize the subject's health and results in either a medical or surgical intervention so as to prevent one of the outcomes listed above.

Important medical events that may not result in death, be life-threatening, or require hospitalization may be considered serious when, based upon appropriate medical judgment, they may jeopardize the patient or subject and may require medical or surgical intervention to prevent one of the outcomes listed in this definition. Examples of such medical events include allergic bronchospasm requiring intensive treatment in an emergency room or at home, blood dyscrasias or convulsions that do not result in inpatient hospitalization, or the development of drug dependency or drug abuse. [Consistent with 21 CFR 312.32 (a)]

Exclusions to the SAE definition for purposes of this study will include:

- Planned admissions to the hospital or elective procedures for pre-existing conditions, which occur during the course of study participation, will not be considered as SAEs.
- Adverse events which result in admission or observation at a hospital for 23 hours or less, will not be considered serious unless they also meet one of the other SAE definition criteria (e. g. deemed to jeopardize the subject's health and results in either a medical or surgical intervention.

8.3.3 EVENTS OF SPECIAL INTEREST

A graft failure will be considered an Adverse Event of Special Interest (AESI) in the MiACL trial. Graft failures will be diagnosed by the patient's physician using a combination of objective laxity (e.g. positive pivot shift) and/or MR imaging. Any such diagnosis, whether treated with an ACL reconstruction revision or not, will be characterized as an AESI. A graft failure is being considered as an AESI as the ACL graft could potentially be impacted by the interventions of interest in the study. As such, a higher than suspected number of ACL graft failures in either group could suggest the active or placebo interventions are compromising the graft tissue/ACL reconstruction and are

unsafe. It is expected that ~10% of ACL grafts will fail with autograft ACL reconstruction and standard ACL rehabilitation.

8.3.4 CLASSIFICATION OF AN ADVERSE EVENT

8.3.4.1 SEVERITY OF EVENT

The intensity of all AEs will be graded using a five-point grading scale in which the following descriptions of severity will apply. Note that for some AEs, Grades 4 and/or 5 may not be applicable. In those cases only 3 different grades (Grade 1-3) are to be considered:

- **Mild (Grade 1)** – Events require minimal or no treatment and do not interfere with the participant's daily activities.
- **Moderate (Grade 2)** – Events result in a low level of inconvenience or concern with the therapeutic measures. Moderate events may cause some interference with functioning.
- **Severe (Grade 3)** – Events interrupt a participant's usual daily activity and may require systemic drug therapy or other treatment. They are medically significant but not immediately life-threatening. Of note, the term "severe" does not necessarily equate to "serious".
- **Life-threatening (Grade 4)** – Events result in life-threatening consequences; urgent intervention indicated.
- **Fatal (Grade 5)** – Events result in death.

8.3.4.2 RELATIONSHIP TO STUDY INTERVENTION

All adverse events (AEs) must have their relationship to study intervention assessed by the clinician who examines and evaluates the participant based on temporal relationship and his/her clinical judgment. The degree of certainty about causality will be graded using the categories below. In a clinical trial, the study product must always be suspect.

- **Definitely Related:** The AE is known to occur with the study interventions/procedures, follows an obvious sequence of time from the study intervention or procedure, the event ceases on discontinuation of the study intervention or procedure (and reoccurs on restarting), and/or the event includes data that was only collected for this study
- **Probably Related:** The AE is lesser known or suspected to occur with the study interventions/procedures, follows a reasonable sequence of time from the study intervention or procedure, and the event ceases or diminishes with discontinuation of the study intervention or procedure.
- **Possibly Related:** The AE is lesser known or a possible effect of the study interventions/procedures, occurs in sequence of time from the study intervention or procedure, for which the event may be attributed to the study intervention or procedure, and/or the event could be explained by the characteristics of the population of study (i.e. young or middle-aged adults, person who have suffered an ACL injury and underwent a subsequent ACL reconstruction)
- **Unlikely Related:** The AE is not a previously known or a suspected effect of the study intervention or procedure, does NOT follow a sequence of time from the study intervention or procedure, for which the event could be attributed to the administration of the study intervention or completion of any study procedure, and/or the event can be readily explained by the characteristics of the population under study.

- **Unrelated:** The AE is not known to be an effect of the study intervention or procedure, does NOT follow a sequence of time from the study intervention or procedure, for which the event could be attributed to the administration of the study intervention or completion of any study procedure, and/or the event can be readily and easily explained by the characteristics of the population under study. An event would also be considered unrelated, if a subject never received study drug, study device, or underwent research study procedure.

8.3.4.3 EXPECTEDNESS

The Principal Investigator or designee will be responsible for determining whether an AE is expected or unexpected. An AE will be considered unexpected if the nature, severity, or frequency of the event is not consistent with the risk information previously described for the study intervention in the protocol or informed consent.

8.3.5 TIME PERIOD AND FREQUENCY FOR EVENT ASSESSMENT AND FOLLOW-UP

A consistent methodology for eliciting AEs will be used at all subject evaluation time points that includes open-ended questions such as:

- “How have you felt since your last clinical visit?”
- “Have you had any new or changed health problems since you were last here?”

The occurrence of an adverse event (AE) or serious adverse event (SAE) may come to the attention of study personnel during study visits and interviews of a study participant presenting for medical care, or upon review by a study monitor. AEs may also be identified through medical record review or through physician evaluation.

All AEs including local and systemic reactions not meeting the criteria for SAEs will be captured on the appropriate case report form (CRF). Information to be collected includes event description, time of onset, clinician's assessment of severity, relationship to study product (assessed only by those with the training and authority to make a diagnosis), and time of resolution/stabilization of the event. All AEs occurring while on study must be documented appropriately regardless of relationship. All AEs will be followed to adequate resolution.

Any medical condition that is present at the time that the participant is screened will be considered as baseline and not reported as an AE. However, if the study participant's condition deteriorates at any time during the study, it will be recorded as an AE.

Changes in the severity of an AE will be documented to allow an assessment of the duration of the event at each level of severity to be performed. AEs characterized as intermittent require documentation of onset and duration of each episode.

All reportable events with start dates occurring any time after informed consent is obtained until the last study visit (i.e. 18 month study visit). At each study visit, the investigator will inquire about the occurrence of AE/SAEs since the last visit. Events will be followed for outcome information until resolution or until last study visit. In the event that an AE or SAE occurred at the last study visit it would be followed for 7 days (non-serious AEs) or 30 days (serious AEs) after said study visit.

8.3.6 ADVERSE EVENT REPORTING

All adverse events (AEs), whether observed by the investigator or reported by the participant, are recorded in the study database by study coordinators. For each AE, the date of onset, severity, and duration is recorded on the electronic case report form (eCRF). In addition, the

investigator or designee will assess whether the AE is serious or not, relationship to study intervention, and whether it is expected or not. All AEs will be monitored and followed until they are adequately resolved or until the end of the study (i.e. 18 month study visit). All AEs must be submitted to the database via the AE eCRF within 72 hours of first knowledge of the event. There will be a special form that is completed for serious adverse events; see Section 8.3.6 below.

8.3.7 ADVERSE EVENT OF SPECIAL INTEREST REPORTING

If a graft failure, the only AESI for the current study, is identified by the study team through patient reporting or review of medical records it will be monitored and reported using the guidelines discussed in section 8.3.5. If the graft failure, however, results in an ACL revision reconstruction this would result in an SAE which would be monitored and reported as discussed in section 8.3.7. Whether designated as an AE or an SAE the AESI will be flagged and specifically reported to the DSMB providing details regarding the number for each study group, and a breakdown of how the AESIs were thought to occur (traumatic or atraumatic). The AESIs will be followed for outcome information until resolution (e.g. date of revision surgery), stabilization (e.g. end of care for the AESI), or study completion, with stop dates recorded for resolution.

8.3.8 SERIOUS ADVERSE EVENT REPORTING

All SAEs will be mapped to system organ classes (SOC) using preferred MedDRA SOC terms, graded for severity and relationship to study drugs as detailed above, and recorded with start dates occurring any time after informed consent is obtained until 30 days after the last day of study participation. At each study visit, the investigator or designee will inquire about the occurrence of SAEs since the last visit and study participants, and their significant others will be asked in advance to notify the study investigators immediately regarding any hospitalization, serious change in their health or in the event of a death. Events will be followed for outcome information until resolution or stabilization, with stop dates recorded for resolution.

Regardless of whether the SAE is deemed related to use of the study interventions, the data for the SAE must be reported with the appropriate information by the study investigators or their designee to the Data Coordinating Center within 24 hours of learning of the event. In addition, new follow-up data must be reported within 24 hours of receipt. The designated study medical monitor, [name], DO, or designee may be contacted at any time for immediate discussion regarding such an event.

Hospitalizations for the following reason, which are not related to an AE, do not require reporting:

- Hospitalization or prolonged hospitalization for diagnostic or elective surgical procedures for preexisting conditions.

When recording a death, the event, or condition that caused or contributed to the fatal outcome should be reported as the single medical concept. If the cause of death is unknown and cannot be ascertained at the time of reporting, the report will be identified as an "Unexplained Death".

Investigators must report all SAEs to their governing IRB/IEC, as required by local regulations and guidelines.

A record of all SAEs, by study subject and preferred SOC terms will be recorded centrally by the DCC.

8.3.9 REPORTING EVENTS TO PARTICIPANTS

We will notify participants of any safety information that modifies the risk profile and may change their willingness to continue in the study. Changes in risk profile or study design affecting participant safety will be addressed via protocol amendment. This information would be reviewed with active subjects who would be asked to sign the amended consent to continue study participation.

8.3.10 REPORTING OF PREGNANCY

If a participant were to report a pregnancy during the study period the interventions would be stopped and follow-up would be discontinued.

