7.1 DISCONTINUATION OF STUDY INTERVENTION

Study interventions may be discontinued for any of the following reasons:

- Unacceptable toxicity (this may include serious adverse events [SAEs] related to study treatment)
- Participant request or withdrawal of consent
- Pregnancy
- Investigator discretion

In instances where participants elect to discontinue NMES treatment per protocol, the following procedure will be followed:

- 1) Participant will be asked if they would be willing to continue with NMES at a maximum tolerated dosage. If yes, patient will continue trial with NMES at this revised dosage. If no, go to #2.
- 2) Participant will be asked if they would be willing to continue with the ECC treatment only (i.e., discontinue NMES, but remain in the study and only receive ECC per protocol). If yes, participant will continue in trial only completing ECC. If not, go to #3
- 3) Participant will be asked if they would be willing to continue being followed to gather study-related measurements, but receive no study-related interventions. If yes, participant will continue in trial only being measured as outlined in the study protocol. If no, participant will be withdrawn from the study as requested.

Consistent with the intention-to-treat principle, randomized participants who permanently discontinue study interventions will continue in the study, and remaining study procedures may be completed as indicated by the study protocol. The data to be collected at the time of study intervention discontinuation will include the following:

- In any participant who does not complete study interventions, we will attempt to gather MRI, strength, and biomechanical data at the 18 month study time-point. Of note, these participants will not be considered SOC control group participants for future study conduct or analyses.

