7.2 PARTICIPANT DISCONTINUATION/WITHDRAWAL FROM THE STUDY

Participants are free to withdraw from participation in the study at any time upon request.

An investigator may discontinue or withdraw a participant from the study for the following reasons:

- Pregnancy
- Significant study intervention non-compliance

- If any adverse event (AE), or other medical condition or situation occurs such that continued participation in the study would not be in the best interest of the participant
- If the participant meets an exclusion criterion (either newly developed or not previously recognized) that precludes further study participation
- Participant is unable to tolerate study intervention dosage
- Due to COVID-19, or any other pandemic crisis

The reason for participant discontinuation of study intervention will be recorded on the Treatment Status Case Report Form (CRF). Withdrawal from the study will be recorded on the Final Status CRF. Participants who were discontinued from treatment due to COVID-19 or other pandemic crisis may be replaced.

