In order to account for physical activity occurring between the 9 and 18 month testing visits, study staff will email participants a physical activity assessment questionnaire at 12 and 15 months post-ACLR. The assessment will include a modified Marx Questionnaire. The Marx Questionnaire will be modified to reflect a 3-month period rather than a 12-month period. This assessment will also inquire about specific sports/activities that study enrollees are participating in.

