9.3 POPULATIONS FOR ANALYSES

Several analysis sets will be used in analyses:

- The main population for efficacy will be the modified intention-to-treat population (mITT), defined as all participants randomized and receiving at least one study intervention. Subjects will be analyzed by assigned treatment.
- A second analysis set will be used to assess the robustness of the primary conclusions in the subset of participants in the mITT analysis set. This set contains participants who complied with the protocol sufficiently to ensure that these data would be likely to represent the effect of treatment according to the underlying scientific model. The Per Protocol (PP) analysis set will consist of all subjects in the mITT population who do not have a major protocol violation, inclusive of violation of entry criteria.
The Safety Population is defined as all participants who are randomized and receive at least study intervention. The Safety Population will be used for all safety analyses. Subjects will be analyzed by assigned treatment.
- All participants in the SOC control group will be included in the exploratory analyses.

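### Section 8.3.10 ends all follow-up on a reported pregnancy, while Section 7.1 keeps such randomized participants in the study and Section 7.2 only permits withdrawal; obtainable mITT data and usually the pregnancy outcome are lost

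*Combined protocol and SAP*

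**What the plan says.** Three sections deal with a pregnancy during the study.

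- Section 8.3.10: "If a participant were to report a pregnancy during the study period the interventions would be stopped and follow-up would be discontinued". No exception is given.
- Section 7.1 lists pregnancy among the reasons for stopping the study intervention. Citing intention-to-treat, it says that randomized participants who permanently stop "will continue in the study, and remaining study procedures may be completed as indicated by the study protocol". It adds: "In any participant who does not complete study interventions, we will attempt to gather MRI, strength, and biomechanical data", at 18 months. It makes no exception for pregnancy.
- Section 7.2: "An investigator may discontinue or withdraw a participant from the study for the following reasons". Pregnancy is the first reason listed.

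Other sections bear on the consequences. Section 9.3 defines the main efficacy set (mITT) as "all participants randomized and receiving at least one study intervention", analyzed by assigned treatment. Section 3 makes KOOS at 9 and 18 months a secondary endpoint. Section 8.1 says that "study staff will email participants a physical activity assessment questionnaire at 12 and 15 months post-ACLR". Section 8.3.2 includes among the SAE criteria "Results in a congenital anomaly/birth defect". Section 8.3.8 records SAEs with start dates "until 30 days after the last day of study participation".

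**The concern.** The instructions for one event differ. For a pregnancy before the interventions are complete, 7.1 keeps the participant in the study and 8.3.10 ends her follow-up. For a pregnancy at any time, 7.2 leaves withdrawal to the investigator and 8.3.10 makes it automatic. Handling could then differ from one participant to the next.

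The rule is also wider than its evident purpose. There is good reason to stop stimulation, loaded exercise, imaging, hop tests or biopsy in pregnancy. Ending all follow-up also removes KOOS, the other questionnaires, the 12- and 15-month forms, and scheduled inquiry about adverse events, including graft failure, the trial's one event of special interest. One intervention session places a randomized participant in the mITT set, so the protocol itself would create missing outcomes in its primary analysis population.

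Finally, no section provides for learning how the pregnancy ended, although a birth defect is a listed SAE criterion.

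**Working it through.** **1. The sections side by side**

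| Situation | 7.1 | 7.2 | 8.3.10 |
|---|---|---|---|
| Pregnancy before interventions are complete (up to about day 126, Section 1.4) | Stays in study; 18-month data sought | Investigator may withdraw | Follow-up ends |
| Pregnancy after interventions are complete (to day 540) | Not addressed | Investigator may withdraw | Follow-up ends |

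In the first row, 7.1 and 8.3.10 cannot both be followed. In the second row no intervention is left to stop, so the only effect of 8.3.10 is to end data collection.

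**2. Could later visits still take place?** In some cases, yes. A pregnancy reported at gestational week 6 on day 302 reaches a 40-week birth on day 302 + 34 × 7 = 540. The 18-month visit window is ±30 days and so runs to day 570. For that report or an earlier one, an 18-month visit after delivery is possible in principle, subject to clinical clearance.

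**3. SAE window.** Assume that the last day of participation is the day of the report.

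- Latest report week that still captures the birth = (week of birth) − 30/7. For a 40-week birth: 40 − 4.3 = 35.7. For births at 37 and 42 weeks: 32.7 and 37.7.
- Days from window close to a 40-week birth = (40 − report week) × 7 − 30. Report at week 6: 238 − 30 = 208 days. Report at week 20: 140 − 30 = 110 days.

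**4. Number affected.** The documents give no pregnancy rate. Assumptions: 40 to 60% of the 112 are female, and 1 to 5% of them conceive per year. Number = 112 × (share female) × (yearly rate) × (years).

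| Period | Low | High |
|---|---|---|
| Whole follow-up, 1.5 years | 112 × 0.4 × 0.01 × 1.5 = 0.7 | 112 × 0.6 × 0.05 × 1.5 = 5.0 |
| Up to 9 months, 0.75 years | 112 × 0.4 × 0.01 × 0.75 = 0.3 | 112 × 0.6 × 0.05 × 0.75 = 2.5 |
| Intervention period, 126/365 = 0.345 years | 112 × 0.4 × 0.01 × 0.345 = 0.15 | 112 × 0.6 × 0.05 × 0.345 = 1.2 |

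Each participant is 1/112 = 0.9% of the planned randomized sample, or about one of the 112 × 0.20 = 22 losses that Section 9.2 allows for.

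**5. Power.** Inputs from Section 9.2: effect size 0.7, two-sided 0.025, 45 evaluable per arm after 20% drop-out (56 × 0.8 = 44.8). The method is the two-sample t-test with noncentrality 0.7 × √(n/2) and 2n − 2 degrees of freedom.

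| Evaluable per arm | Losses beyond the allowance | Power |
|---|---|---|
| 45 | 0 | 84.9% |
| 43 | 4 | 83.0% |
| 42 | 6 | 82.0% |

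The first row reproduces the plan's claim of at least 80%. The claim still holds in the other two rows.

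**The case against.** The strongest reply is that 8.3.10 is the specific rule and governs the general one in 7.1. Section 7.2 already allows withdrawal for pregnancy, and also for a newly developed exclusion criterion that precludes further participation. A permission in 7.2 and a direction in 8.3.10 are not strictly contradictory. On size, Section 5.2 excludes women who are pregnant or planning pregnancy, and a baseline urine test is required, so the assumed conception rates may be too high. The direct conflict with 7.1 is confined to the intervention period, with roughly 0.15 to 1.2 participants. The documents do not show that isokinetic strength testing is feasible in pregnancy, so the loss of primary-endpoint data is not demonstrated. The interventions are electrical stimulation and leg press, not a drug, so the pregnancy outcome may tell little. Capture is not impossible either: 8.3.8 asks participants in advance to report hospitalization or a serious change in health, and 8.3.5 allows review of medical records. The manual of operations and the consent forms, which were not available, may add detail.

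Much of this stands as a limit on size. It does not remove the point. Section 7.1 names pregnancy itself and carves out no exception, so nothing in the text tells staff which section prevails. If 8.3.10 does prevail, the plan deliberately discards questionnaires and event inquiry that pregnancy does not prevent, and strength tests where clinicians would permit them. Advance notification and record review do not lengthen the 30-day SAE window.

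**Conclusion.** The concern holds. Followed as written, 8.3.10 turns some obtainable mITT outcomes into missing data and usually leaves the pregnancy outcome unrecorded, and during the intervention period it conflicts with 7.1. The mITT point applies to randomized participants only, not to the standard-of-care group.

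The efficacy consequence is small. Few participants are affected on any of the assumed rates, age and gender are in the primary model, multiple imputation is planned (Section 9.4.2), and power stays above 80%. The main efficacy conclusion is unlikely to change. The text comparison rests on no assumption. The counts rest on assumed rates, and the SAE-window figures on participation ending on the day of the report. This is a recommended correction, not an essential one; its benefit is consistent handling, fewer avoidable missing values and a recorded pregnancy outcome.

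**What to change.** Reword 8.3.10 and align 7.1 and 7.2 with it:

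- A reported pregnancy stops the study interventions, and imaging as clinically indicated, but does not end follow-up.
- Unless the participant withdraws consent, continue the questionnaires, the emailed 12- and 15-month forms, adverse event review, and any assessment her clinicians permit.
- Report the pregnancy to the Data Coordinating Center and record its outcome through one later contact.

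The cost is wording in three sections, one extra contact per pregnancy, and possibly a consent line allowing that contact (the consent pages were not available to check). The downside is a few partial 9- or 18-month visits. No change to the design or sample size is needed.
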